6.7 Multicenter Study

This is a multicenter study. The primary analysis will have all sites pooled. When appropriate, the by-country summaries may be presented. Response rates will be compared between the two participating countries, Germany and US.

6.8 Multiple Comparisons/Multiplicity Adjustment

Not applicable because no formal statistical analysis and hypothesis tests are planned.

6.9 Examination of Subgroups

If sample size allows, primary and key secondary efficacy variables may be summarized by subgroup to explore the heterogeneity of the treatment effect across subgroups. Subgroups that might be considered are:

- Gender (Male, Female)
- Age (<30, 30 to <55, 55+)

7. Statistical Analysis

7.1 Analysis Populations

The population of “all enrolled subjects” consists of all subjects who signed informed consent, met all eligibility criteria at Screening, and having received the first dose of the study drug.

7.1.1 Modified Intent-to-treat Population

The modified intent-to-treat (MITT) population will consist of all subjects who are enrolled, have received at least one dose of study drug and have at least one post-baseline assessment for the primary efficacy variable UCT.

7.1.2 Safety Population

The safety population will consist of all subjects who signed informed consent, met all eligibility criteria at Screening, and having received at least one dose of study drug.

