Concomitant Medications	Second-generation H1-antihistamines as concomitant medication once daily and up to 4 times daily on demand (drug intake to be documented in the patient diary).
Safety Evaluations	
Safety and tolerability will be assessed throughout the study by monitoring and evaluating adverse events (AEs), including any complications resulting from the IV infusion. All treatment-emergent adverse events (TEAEs) will be collected from the start of study drug administration through 8 weeks after last dose received or Early Termination (ET). Severity will be assessed using the National Cancer Institute (NCI) Common Terminology Criteria for Adverse Events (CTCAE) Version 4.03. All AEs will be assigned a severity grade and relationship to study drug.
 
Additional safety evaluations include clinical laboratory tests, including anti-drug antibody to AK002, complete blood counts, chemistries, and urinalyses, ECGs; and vital signs.

Statistical Methodology	All subjects who received a dose of study drug will be included in the analysis. All safety data will be listed. Where appropriate, summary statistics will be provided (number of non-missing values, mean, median, standard deviation, minimum, and maximum for continuous variables, and number and percentage for categorical variables) for all measures, including demographic and baseline values, clinical scores and safety endpoints.
Rationale for Amendment 4.1	
The following modifications have been incorporated into Amendment 4.1 of the protocol.
 
 
• Procedures that allow subjects in the CholU, UF, and CSU-XOLAIR® (omalizumab) failure cohorts who received all 6 infusions of AK002, were followed through Day 155, and demonstrated severe symptoms of urticaria following discontinuation of treatment, to be offered the option to receive extended dosing with up to 12 additional doses of AK002. Offering extended dosing allows subjects with no other treatment options continued access to AK002 and the benefit obtained during the initial 6 infusions. It also allows for collection of longer-term efficacy, safety, and tolerability data of AK002.
 
• PK will be analyzed retroactively using backup blood samples.
 

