#### 6.1.1 Screening Period

At the beginning of the screening period, eligible subjects will be asked to sign the informed consent form (ICF) and their current medication will be discussed. During the screening period, subjects will continue with their current antihistamine medication (approved dose). Subjects who do not meet all eligibility criteria at Screening, or who qualify at Screening but are not enrolled, may be assigned a new Patient ID number and re-screened once. Subjects re-screened within

30 days of signing the initial consent will not need to sign a new ICF providing there have been no changes to the ICF. A patient is considered enrolled in the trial when the patient receives their first dose of AK002.

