### **13. Data Analysis**

This section outlines the statistical methods to be used for the analysis of the data from the study. A separate Statistical Analysis Plan (SAP), which will be completed and signed off prior to data base lock.

When the SAP differs from analyses described in the protocol, the SAP will take precedence.

Continuous variables will be summarized using number of non-missing observations, mean, standard deviation (SD), median, minimum, and maximum; categorical variables will be summarized using the frequency count and the percentage of subjects in each category.

Baseline for data analysis is defined as the last assessment prior to the first infusion of the study drug.

The primary summaries will be based on individual cohorts and the data from all 3 cohorts combined, wherever possible.

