### **13.1.2 Safety Population**

The safety population will consist of all subjects who are enrolled, have received at least one dose of study drug.

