3.7 Changes to Analyses Planned in the Protocol

None.

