3.9.9 Prior, Concomitant, and Prohibited Medications

Prior medications and concomitant medications will be extracted from the Prior/Concomitant Medication CRF. Medications taken prior to Study Day 1 will be considered as prior medications and medications taken on or after Study Day 1 will be considered as concomitant medications. Prior and concomitant medications will be coded using WHO Drug Dictionary (WHODD March 2018 release) for Preferred Term (PT) and Anatomical Therapeutic Chemistry (ATC) classification.

Prohibited medications include, but are not limited to,

- Omalizumab
- H2-antihistamines
- Routine (daily or every other day during 5 or more consecutive days) doses of systemic corticosteroids
- Routine (daily or every other day during 5 or more consecutive days) doses of systemic hydroxychloroquine
- Routine (daily or every other day during 5 or more consecutive days) doses of methotrexate, cyclosporine A, cyclophosphamide, tacrolimus and mycophenolate mofetil
- Intravenous immunoglobulin G
- Plasmapheresis
- Regular (daily or every other day) doxepin (oral)
- Inactive vaccination
- Live attenuated vaccine
- Leukotriene Antagonists

4. Definitions

Table 4 Terminology and Definition

Terminology	Definition
Study Medication/Drug (SM)	AK002 administered by IV infusion.
Study Day	The first dose date (Day 1) is defined as the date on which a subject took the first dose of study medication (SM). Other study days are defined relative to Study Day 1. For visits prior to the first dose of the SM, Study Day is calculated as Visit Date – Day 1. For visits after the first dose, Study Day is calculated as Visit Date – Day 1 +1.
Enrolled	Subject who has signed informed consent, met all eligibility criteria at Screening, and having received the first dose of the study drug.
Completer for the Study	Subject who completes End of Study visit
Baseline	Baseline is defined as the non-missing value collected most recent to and before the time of the very first dose of the SM.
Prior Medication	Medication collected on the Prior/Concomitant Medication CRF, with start date prior to Study Day 1.
Concomitant Medication	Medication collected on the Prior/Concomitant Medication CRF, with end date on/after Study Day 1.
Treatment-emergent	Adverse events with onset date on or after the start of first study drug administration.

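### The SAP adds an undeclared eligibility condition to the Enrolled and Safety sets, so a dosed patient who failed a Screening criterion belongs to no analysis population

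*SAP*

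**What the plan says.** **Protocol.** Three statements cover every dosed patient, and none carries an eligibility condition.
- Section 6.1.1: "A patient is considered enrolled in the trial when the patient receives their first dose of AK002".
- Section 13.1.2: "The safety population will consist of all subjects who are enrolled, have received at least one dose of study drug".
- Synopsis, Statistical Methodology: "All subjects who received a dose of study drug will be included in the analysis".

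**SAP.** The same eligibility condition is joined to dosing in three places.
- Section 4, definition of Enrolled: "Subject who has signed informed consent, met all eligibility criteria at Screening, and having received the first dose of the study drug".
- Section 7.1, the all-enrolled set: consenting subjects who "met all eligibility criteria at Screening, and having received the first dose of the study drug".
- Section 7.1.2, Safety: consenting subjects who "met all eligibility criteria at Screening, and having received at least one dose of study drug".

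**Which text governs.** Protocol Section 13 states: "When the SAP differs from analyses described in the protocol, the SAP will take precedence". SAP Section 1 likewise says that the SAP supersedes the protocol's statistical methods. Under the SAP heading "Changes to Analyses Planned in the Protocol" (3.7) the only entry is None.

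**The concern.** A safety population should contain everyone exposed to the drug. An eligibility condition removes patients for a reason unrelated to exposure, and here it does so without being declared.

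The SAP makes safety part of its primary objective (2.1). Under the literal reading, the affected patient drops out of every summary tied to these sets:
- disposition table and listing (7.2);
- demographics (7.4) and baseline disease characteristics (7.5);
- exposure and compliance (7.6.1);
- prior and concomitant medication (7.6.2).

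SAP 7.10.1 names no population for the AE incidence tables. Safety is the natural one, and on that reading the patient is missing there too. The AE listings cover all events, so tables and listings would not reconcile, and the reported incidence would not cover everyone exposed. Section 8 says the extension will be analysed almost identically, so the wording carries over.

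**Working it through.** The plan states no figure on this point, so there is nothing to reproduce. The check compares definitions, traces one patient through them, and then illustrates the size.

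**1. Definitions side by side**

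| Set | Protocol | SAP |
|---|---|---|
| Enrolled | First dose received (6.1.1) | Consent + all eligibility criteria met at Screening + first dose (Section 4, 7.1) |
| Safety | Enrolled + at least one dose (13.1.2) | Consent + all eligibility criteria met at Screening + at least one dose (7.1.2) |
| MITT | Enrolled + at least one dose + a post-baseline Urticaria Control Test (UCT) score (13.1.1) | Same words (7.1.1), but with the SAP's meaning of enrolled |
| Per-protocol | MITT without major violations (13.1.3) | Same (7.1.3) |

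**2. One patient traced through**

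Take a patient who consented and was dosed, but whose HIV serology at Screening is later found to have been positive (exclusion 20).

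| Set | Protocol | SAP, literal |
|---|---|---|
| Enrolled | Yes | No |
| Safety | Yes | No |
| MITT | Yes, given a post-baseline UCT | No |
| Per-protocol | Depends on deviation review | No |

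The SAP foresees such patients: 7.3 lists non-compliance with the entry criteria among the deviations. Protocol 13.3 summarises major deviations, and the only set from which it removes patients is the per-protocol set.

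**3. Reach of the condition**

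It applies to criteria failed at Screening. The 23 exclusion criteria in protocol 7.2.2, sorted by the time each one states:
- screening: 3 (nos. 5, 19, 20);
- no visit named: 9 (1, 3, 4, 6, 7, 8, 9, 10, 23);
- Baseline: 8 (2, 11, 12, 13, 14, 15, 18, 21; no. 21 also mentions screening);
- enrolment: 2 (16, 17);
- dosing: 1 (22).

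Check: 3 + 9 + 8 + 2 + 1 = 23, of which 8 + 2 + 1 = 11 are tied to Baseline, enrolment or dosing. Protocol Table 3 marks eligibility at Visit 1 and again at Visit 2. A failure found only at Visit 2 is not clearly covered.

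**4. Size, as an illustration**

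Inputs: about 48 subjects in four cohorts of about 12 (SAP 3.3). The number k of dosed patients who failed a Screening criterion is an assumption, k = 1 to 3.

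Share removed, k/48: 1/48 = 2.1%; 2/48 = 4.2%; 3/48 = 6.3%.

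Exact (Clopper-Pearson) two-sided 95% limits for x events in n subjects:
- x = 0: lower 0, upper 1 − 0.025^(1/n);
- x ≥ 1: lower is the 0.025 quantile of Beta(x, n − x + 1), upper is the 0.975 quantile of Beta(x + 1, n − x).

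Suppose each of the k patients has the event and nobody else does:

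| k | All dosed patients | SAP, literal |
|---|---|---|
| 1 | 1/48 = 2.1% (0.05 to 11.1%) | 0/47 (0 to 7.5%) |
| 2 | 2/48 = 4.2% (0.5 to 14.3%) | 0/46 (0 to 7.7%) |
| 3 | 3/48 = 6.3% (1.3 to 17.2%) | 0/45 (0 to 7.9%) |
| 1, within one cohort | 1/12 = 8.3% (0.2 to 38.5%) | 0/11 (0 to 28.5%) |

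For example, the upper limit for 0/47 is 1 − 0.025^(1/47) = 0.0755.

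**The case against.** **The clause may only describe the normal path into the trial.** Protocol 6.1.1 and 9.5 and the SAP's schedule notes use nearly the same phrase to separate screen failures from those who qualify. SAP 3.3 says that those enrolled meet the entry criteria. On this view the clause means passed screening and was then dosed. SAP 7.3 and 7.1.3 fit that view, because they treat eligibility violations as something found among analysed subjects. The literal reading is also hard to apply: inclusion 9 (UCT below 12) is judged at enrolment, yet no UCT is scheduled at Visit 1, and inclusion 10 concerns extended dosing and needs Week 22 data.

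This is plausible and may well be what was intended. The text does not say so, however, and the condition appears three times in definitions that a programmer would code. That it is hard to apply is a further reason to remove it.

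**The harm is conditional.** It needs an ineligible patient to be dosed, a failure at Screening, literal programming, and AE tables run on the Safety set. The numerical example also needs that patient to have the only case. The study is descriptive, with no hypothesis tests. Data would still be listed: SAP 6.1 lists all available data and 7.10.2 lists laboratory results for all subjects. All of this stands. It confines the problem to summary tables and their denominators.

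**The count of criteria goes by wording, not by when the test is done.** Exclusions 18 and 21 are worded for Baseline, although stool and serology are scheduled only at Visit 1. Inclusion criteria are not counted. This is fair: the count shows that the clause is ambiguous and does not bound how many patients it could reach.

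**Conclusion.** The concern holds. The SAP's Safety and Enrolled definitions are narrower than the protocol's, the SAP governs, and the change is not declared. Followed as written, they leave a dosed patient who failed a Screening criterion outside every defined population and give a wrong safety denominator.

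The size depends on a count that the documents do not give. With no such patient there is no effect. With one, 2.1% of 48 dosed subjects are removed, and a sole event disappears from the table (0/47 instead of 1/48, or 0/11 instead of 1/12 in a cohort). These figures assume 48 dosed subjects, a literal reading, and AE tables based on the Safety set. The mismatch in the text is certain; the consequence is conditional. It should be fixed before the analysis is programmed.

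**What to change.** - **SAP 7.1.2:** define Safety as all subjects who received any amount of AK002, whether or not they met the eligibility criteria. At a minimum, delete the eligibility condition; the consent condition can stay.
- **SAP Section 4 (Enrolled) and 7.1:** delete the same condition so that enrolment matches protocol 6.1.1. This also corrects MITT, which relies on the term.
- **SAP 7.10:** add one sentence stating that all safety tables use the Safety population.
- **Eligibility violations:** exclude patients for major violations only from the per-protocol set (7.1.3), and add this to Appendix A, which does not list it now. Keep the deviation listing in 7.3.
- **SAP 3.7:** if any difference from the protocol's populations is kept on purpose, record it there with the reason.

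The cost is one clause removed in three places, one sentence in 7.10 and one line in Appendix A. No new data or analyses are needed. If the harmless reading was intended, the edit changes nothing in practice.

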7.1.3 Per-Protocol Population

The Per-Protocol (PP) population may be considered for the summary. The PP population will consist of all subjects from the MITT-population for whom no major protocol violations adversely affecting the data interpretation are reported.

7.2 Disposition of Subjects

Subjects (n and %) who completed or discontinued from the study will be tabulated by cohort and overall using all enrolled subjects. The primary reasons for study discontinuation will be included in the tabulation. The primary reasons may include any of the following:

- Subject withdrew consent
- Lost to follow-up
- Administrative reason
- Adverse event
- Investigator decision
- Failure to follow required study procedures
- Other

Subject disposition will be summarized for all Enrolled Subjects, MITT, Safety, and PP populations. A data listing will be presented for all enrolled subjects.

7.3 Protocol Deviations

Protocol deviations will include, but are not limited to

- Non-compliance with scheduled study visit
- Non-compliance with study treatment
- Prohibited medications
- Non-compliance with study inclusion or exclusion criteria
- Non-compliance with study assessment procedures

Protocol deviations will be reviewed and classified as major or minor based on their effect on the integrity of the study. Subjects with major protocol deviations will be listed. The listing will include a brief description of the deviation, deviation category, and if applicable, study day when deviation occurred along with other pertinent information.

7.4 Demographics and Baseline Subject Characteristics

Descriptive statistics of subject characteristics and baseline values will be presented by cohort and overall using the MITT and Safety populations.

All demographic and baseline characteristics will be included in the subject data listing.

7.5 Baseline Disease Characteristics

Summaries of baseline disease characteristics will be based on the Safety population.

Subject incidence (n and %) of medical history (and current medical condition present before signing the informed consent) will be tabulated by MedDRA System Organ Class (SOC) and Preferred Term (PT). Subject smoking habits will also be tabulated.

All baseline disease characteristics will be listed.

7.6 Treatments

7.6.1 Treatment Compliance and Extent of Exposure

Summaries of treatment compliance and exposure for AK002 and second generation of H1-antihistamine will be based on the safety population.

Duration of exposure is defined as the total number of days a subject is exposed to the study treatment. This will be calculated for each subject by taking the difference between the date of the last dose minus the date of the first dose, plus 1 (date of last dose – date of first dose +1).

Duration of Treatment exposure will be summarized using descriptive statistics (n, mean, standard deviation, median, minimum, and maximum).

Subjects will be tabulated with n (%) by the number of doses they received.

7.6.2 Prior and Concomitant Medications

Prior and concomitant medications will be tabulated separately based on the Safety Population.

Number (n and %) of subjects taking at least one medication and the number (%) of subjects taking each medication at the WHODD PT level will be tabulated by ATC4 and PT. Subjects taking the same PT medication twice will only be counted once.

A subject data listing will be provided to include the reported medication name, the WHODD PT, ATC4, indication, route, and frequency, study day, and pertinent subject information.

A separate data listing will include subjects who received prohibited medications.

7.7 Efficacy Analyses

7.7.1 Primary Efficacy Analysis

The primary efficacy variable is the change from baseline in UCT score for each population (CSU-XN, CSU-XF, UF, and CholU). UCT score and its change from baseline will be summarized using descriptive statistics by study visit (Weeks 4, 8, 10, 12, 16 for subjects enrolled under Protocol Amendment 2.1 and Weeks 4, 8, 12, 16, 20, 22, 24, and 28 for subjects enrolled after Protocol

Amendment 3). A 95% CI for the mean change will be computed. The summaries will be provided for each cohort.

7.7.1.1 Per Protocol Analysis

This analysis will be conducted by repeating the primary analysis on the per protocol population.

7.7.1.2 Subgroup Analysis

The primary efficacy analysis will be conducted for the gender and age subgroups as defined in Section 6.9.

7.7.1.3 Secondary Efficacy Analyses

All summaries will be provided for each cohort.

- 1) Subjects achieving UCT CR and CMR will be tabulated with % of subjects for each visit. Subjects achieving a maximum of 0, 1, 2, 3, or 4 responses over the 8 post-baseline visits (subjects enrolled under Protocol Amendment 3) will also be tabulated. A 95% CI for the % responses will be calculated using the binomial distribution. Subjects achieving UCT DC will be similarly summarized.
- 2) Changes from baseline in UAS7 in CSU patients will be summarized similarly for each week the diary is collected. A 95% CI for the mean change will be reported. This analysis will also be carried out in the subgroup of CSU-XN patients with baseline UAS7 ≥ 16 .

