Study Design/Phase	This is an open-label, proof-of-concept study.
Objectives	To assess the effects of AK002 on symptom control in subjects with chronic urticaria. CU subjects will document triggers and symptoms (wheals, pruritus, etc.), as well as quality of life (QoL), before, during and after treatment. Subjects will also be subjected to standardized provocation tests and assessment of symptom development.

Primary Objective	To assess the efficacy of AK002 on symptoms in subjects with CU (change in urticaria control test [UCT] score).
Secondary Objectives	The efficacy, safety and pharmacodynamics of AK002 on urticaria symptoms, QoL, provocation testing, and histological criteria.
	The effects of AK002 in CU subjects will be assessed through the following evaluations:
	1) Safety and tolerability (adverse events, laboratory safety tests etc.)
	2) Disease activity scores (UAS7, [REDACTED])
	3) [REDACTED]
	4) Number of symptom-free days
	5) Use of rescue medication (up to 3 sgAH tablets/day)
	6) Effects on [REDACTED]
	7) Number of [REDACTED]
	8) [REDACTED]
	9) Changes in trigger thresholds (in CINDU, including CholU)
	10) Rate of [REDACTED] (UCT, [REDACTED])
	11) Serum levels of potential biomarkers of disease activity and treatment responses
	12) Rates of relapse and sustained response during the follow-up period
Endpoints	
Primary Endpoint	The primary endpoint is the change in Urticaria Control Test (UCT), a score for symptom control in chronic urticaria, from baseline to Week 22 in CU subjects after treatment with AK002. A change of the UCT score of 3 or more points is regarded as clinically relevant (minimal clinically important difference [MCID]).
Other Endpoints	
 
1) Safety of subjects treated with AK002: This includes physical examination, routine safety laboratory assessments, vital signs, electrocardiogram (ECG), urine safety, and adverse event reporting (Visits 2–10)
 
2) Change in disease activity as assessed by UAS7 and/or [REDACTED] from Baseline to Visits 3, 5, 8, and 10
 
3) Change in number of symptom-free days per week (patient diary-based CSU score; wheals, flares, itch, avoidance behavior) from Baseline to Visits 3, 5, 8, and 10
 

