## **13.6 Analysis of the Primary Objectives**

### **13.6.1 Primary Efficacy Variable**

The primary variable is the change from baseline in UCT score. This variable will be summarized using descriptive statistics of mean, median, minimum, and maximum at Weeks 4, 8, 12, 16, 20, 24, and 28. A 95% confidence interval for the mean will be computed. The summaries will be provided for all 3 cohorts combined as well as for each individual cohort.

Additionally, subjects achieving complete response (CR: defined as the total UCT score = 16) will be summarized with number and percent of subjects for each visit. Subjects achieving 0, 1, 2, 3, and 4 CRs over the 7 post-baseline visits will also be summarized. Refer to the SAP for additional information.

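### The SAP's table of UCT response counts stops at 4 although 8 visits are counted, so subjects in unbroken response from Week 16 or earlier have no row

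*SAP*

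**What the plan says.** SAP 7.7.1.3, item 1, covers UCT complete response (CR) and clinically meaningful response (CMR). Besides the percentage of responders at each visit, it calls for a tabulation of "Subjects achieving a maximum of 0, 1, 2, 3, or 4 responses over the 8 post-baseline visits", restricted to subjects enrolled under Protocol Amendment 3. Disease control (DC) gets the same treatment: "Subjects achieving UCT DC will be similarly summarized".

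SAP 7.7.1 names the visits: "Weeks 4, 8, 12, 16, 20, 22, 24, and 28 for subjects enrolled" after Amendment 3, and "Weeks 4, 8, 10, 12, 16 for subjects enrolled under Protocol Amendment 2.1". The count tabulation does not mention the second group.

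Protocol 13.6.1 has a parallel table: "Subjects achieving 0, 1, 2, 3, and 4 CRs over the 7 post-baseline visits will also be summarized". Its visit list is "at Weeks 4, 8, 12, 16, 20, 24, and 28", without Week 22.

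The protocol's secondary objectives (Synopsis and 4.2, item 12) include "Rates of relapse and sustained response during the follow-up period". The readable endpoints and efficacy analyses in SAP 5.1–5.3 and 7.7 contain no relapse or sustained-response analysis, although parts of 5.3 and 7.7.2 are redacted.

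**The concern.** A frequency table should have a place for every value its variable can take. Here the variable can reach 8 and the rows end at 4, with no open-ended top row. The subjects left out are not a random subset: they are the ones who respond earliest and hold the response longest. The more often subjects respond, the more of them fall outside the table.

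This is also the only readable UCT summary in the SAP that follows response within a subject across visits. Visit-by-visit percentages cannot show whether the same people remain in response. At stake is a fair description of repeated response in a pilot whose protocol lists sustained response among its objectives.

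**Working it through.** **1. Reproduce the number of visits.** The SAP 7.7.1 list for subjects enrolled after Amendment 3 (Weeks 4, 8, 12, 16, 20, 22, 24, 28) has 8 entries, matching the 8 in SAP 7.7.1.3. The list in Protocol 13.6.1 has 7, matching the protocol's 7. The Amendment 2.1 list (Weeks 4, 8, 10, 12, 16) has 5.

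**2. Compare possible and listed values.** Over 8 visits the count can take 9 values (0 to 8). The SAP lists 5 (0 to 4) and leaves out 4 (5, 6, 7, 8).

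**3. Count responses for unbroken response to the last visit.** With all visits attended, the count is the number of listed visits from onset through Week 28:

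| Onset week | SAP, 8 visits | Protocol, 7 visits |
|---|---|---|
| 4 | 8, no row | 7, no row |
| 8 | 7, no row | 6, no row |
| 12 | 6, no row | 5, no row |
| 16 | 5, no row | 4, listed |
| 20 | 4, listed | 3, listed |
| 22 | 3, listed | not a listed visit |
| 24 | 2, listed | 2, listed |
| 28 | 1, listed | 1, listed |

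The cap bites from onset at Week 16 or earlier in the SAP, and at Week 12 or earlier in the protocol. On the five-visit Amendment 2.1 schedule, a 0–4 scale would miss only a subject responding at all 5 visits.

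**4. Test the two readings of a maximum of k responses.**
- *Total count, or at most k in total:* every subject with 5 to 8 responses lacks a row.
- *Longest consecutive run:* the number of 8-visit patterns with 5 or more responses is C(8,5) + C(8,6) + C(8,7) + C(8,8) = 56 + 28 + 8 + 1 = 93. Enumeration shows that 73 of them have a longest run of 4 or less and would fit; 20 would not. Step 3's unbroken responders from Week 16 or earlier have runs of 5 to 8 and are among the 20.

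**5. Illustrate the size under the total-count reading.** The documents give neither a per-visit response probability p nor a within-subject correlation ρ, so both are assumed. For ρ = 0, P(X ≥ 5) = Σ C(8,k) p^k (1−p)^(8−k), summed over k = 5 to 8. For ρ > 0, X is beta-binomial with α = p(1−ρ)/ρ and β = (1−p)(1−ρ)/ρ. For example, p = 0.5 and ρ = 0.3 give α = β = 0.5 × 0.7/0.3 = 1.167.

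| p | ρ = 0 | ρ = 0.3 | ρ = 0.6 |
|---|---|---|---|
| 0.3 | 6% | 20% | 26% |
| 0.5 | 36% | 44% | 47% |
| 0.7 | 81% | 70% | 69% |

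These are shares of subjects in the table with complete visits. The model holds p constant across visits, which is a simplification, since the planned dose steps up and then stops.

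**The case against.** The strongest reply is that little is lost. The study is descriptive and tests no hypothesis (SAP 3.5). The same SAP item reports CR and CMR at every visit, with DC likewise, and SAP 6.1 requires individual listings sorted by cohort and subject. In cohorts of about 12, a reader could rebuild the counts. All of this stands, and it keeps the point to table design.

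A second reply is that the share with 5 or more responses is simply what remains to 100%. That works only if the denominator is all subjects in the cohort. SAP 7.7.1.3 does not state a denominator, and SAP 6.1 removes missing values from denominators. Even then the remainder would merge counts of 5, 6, 7 and 8 and could include subjects with missed visits. For the same reason it cannot be said outright that the printed percentages will fail to sum to 100.

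Third, the table shells in SAP Appendix D are not visible in the public copy, so the final row layout cannot be checked. The written rule is nevertheless explicit, and neither document gives a reason for stopping at 4.

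Fourth, the protocol's table is not identical. Its CR is a UCT score of 16, whereas SAP section 4 requires at least 12 plus a rise of at least 3 points. The SAP states that it supersedes the protocol's methods, so the SAP is where the repair belongs.

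One might also object that any such count pools treatment and follow-up visits and that 4-week UCT recall overlaps between closely spaced visits. Adding rows would not change either feature, and the point does not rest on them.

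**Conclusion.** The point holds as a truncation of a descriptive table. Under either reading of the wording, subjects in unbroken response from Week 16 or earlier, with all visits attended through Week 28, have no row. One missed visit after a Week 16 onset would bring the total to 4, which is listed.

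Three stronger readings are tempting but unsupported:

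- *Every subject with 5 to 8 responses is necessarily left out.* This is true for a total count. Under the longest-run reading most such patterns fit, and the SAP does not say which is meant.
- *About 4 to 6 of 12 subjects per cohort would have no row.* A reader might get this by applying 36–47% to 12 (4.4 to 5.7). The SAP confines the table to Amendment 3 subjects, and the number enrolled under Amendment 2.1 is not given, so 12 is a planned upper bound.
- *Evidence of durable response is lost.* Per-visit rates and listings retain it, and neither document labels this count a durability analysis.

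The absence of a readable SAP analysis for the protocol's sustained-response objective is related and can be closed in the same edit. No primary estimate or test is affected. The change is worth making because the omitted subjects are the most consistent responders and the cost is small.

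**What to change.** In SAP 7.7.1.3:

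1. State that the count is the total number of post-baseline visits at which the subject meets the response definition, and drop the phrase that could mean longest run.
2. Tabulate 0 to 8 for subjects on the eight-visit schedule and, separately, 0 to 5 for those on the Amendment 2.1 schedule, for each of CR, CMR and DC.
3. Use the MITT subjects of each cohort on that schedule as the denominator, and show subjects with missing visits explicitly.
4. For the protocol's sustained-response objective, add one row per cohort: among subjects in response at Week 22, the number still in response at both Week 24 and Week 28.

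The cost is some SAP wording and a few more table rows, many holding small counts. No new data are needed.
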